6.3.5 Reporting and Handling of Pregnancies

Pregnant subjects must immediately be withdrawn from the clinical trial. Any pregnancy, in a female subject or female partner of a male subject, identified during the treatment phase of the trial and within 90 days after discontinuation of trial medication must be reported to the Sponsor **within 24 hours** (in the case of a female partner of a male subject this will be within 24 hours after obtaining written informed consent from the pregnant woman). The course and endpoint of the pregnancy should be followed up carefully, and any abnormal endpoint regarding the mother or the child should be documented and reported.

A female subject must be instructed to stop taking the IMP and immediately inform the Investigator if she becomes pregnant. The Investigator will make arrangements for the subject and/or partner to be seen by a specialist who can discuss any risks of continuing with the pregnancy. Monitoring of the subject and the child should continue until 4 weeks after the outcome of the pregnancy is known.

6.3.6 Periodic Reporting of Safety

An annual safety report will be submitted **once a year** to the local IEC/IRB via the local Investigator and to CAs via the Sponsor or CRO.

6.4 Follow-up of Serious Adverse Events

Serious AEs should be followed until resolution or stabilization. Subjects with ongoing SAEs at trial termination (including safety visit) will be further followed up until recovery, return to baseline status, or stabilization. If after follow-up, return to baseline status or stabilization cannot be established, an explanation should be recorded on the eCRF SAE form.

6.5 Abnormal Laboratory Findings and Other Abnormal Investigational Findings

Abnormal laboratory findings and other abnormal investigational findings (for example, on an ECG trace) should not be reported as AEs unless they are associated with clinical signs and symptoms, lead to treatment discontinuation, or are considered otherwise clinically significant by the Investigator. If a laboratory abnormality fulfills these criteria, the identified medical condition must be reported as the AE rather than the abnormal value itself.

Elevations (or new elevations from baseline) in transaminases or tests of liver function will be closely monitored. Laboratory tests (AST, ALT, alkaline phosphatase, gamma glutamyl transaminase, total bilirubin, viral serologies) will be used to distinguish other causes of liver injury from drug-induced liver injury. Subjects with persistent or new deterioration of hepatic function will be followed up.

6.6 Trial Specific Safety Considerations

6.6.1 Overdose

Details of overdose of apaglutide or any concomitant therapy must be recorded in the eCRF and on the dedicated paper form to be included into the Safety Database. Any overdose that is considered by the Investigator to be clinically significant must be reported as an SAE in the eCRF.

6.6.2 Considerations on Investigational Medicinal Product Dose Reduction and Temporary Discontinuation

If the Investigator reduces the dose of the IMP because of documented safety reasons, the safety reasons should be documented as an AE.

Reduction of IMP means reducing the dose by one step (see Table 5) or pausing in case of general tolerability issues. The IMP dose can only be reduced by one step during the trial.

For specific dose adjustments of apaglutide in cases of abnormal liver function tests, bilirubin, or other clinical chemical parameters, refer to Section 4.2. **The Investigator should attempt to return to the per protocol dose as soon as the medical condition of the subject allows and a new weekly schedule of IMP administration may be established.** If the subject does not continue to tolerate the per protocol dose the Investigator may choose to resume IMP administration at the weekly lower dose.

Changes and discontinuations must be reported to the CRA in charge of the site and discussed with the Medical Monitor. If the subject's medical condition allows, this discussion may occur before any dose change/discontinuation but must occur after if not possible (e.g., an AE necessitating an immediate stop to dosing with apaglutide). The final decision to reduce or discontinue IMP rests with the Investigator.

Dose changes and the rationale will be documented in the medical records, and in the eCRF. Missed doses (scheduled doses that have not been taken) will not be made up for, i.e., the treatment period will not be prolonged due to temporary discontinuation. Missed doses should be reported as a protocol deviation.

6.6.3 Trial Holding/Stopping Criteria

The trial will be placed on hold (i.e. screening or randomization of new subjects and treatment of existing subjects should be interrupted) if, during the first 182 days after the start of apaglutide treatment, a subject experiences:

- Emergence of a new GI or hepatobiliary cancer
or
- Undergo major surgical intestinal resection due to a proliferative intestinal phenomenon

Subsequently, an ad-hoc iSRC will review the data and make a recommendation to either continue or stop the trial.

The following toxicity events have been identified for monitoring:

- Apraglutide-related (definitely, probably, possibly) deaths
- Grades 3–4 apraglutide-related (definitely, probably, possibly) organ toxicities
- Any apraglutide or/and RUX administration stop or hold due to elevation of ALT/AST and/or bilirubin as defined in Section 4.2.1.2 and Section 4.2.2.1 (confirmed Hy's law cases)

These events will be monitored in accordance with the Toxicity Guidance Rule outlined in Table 10. If the Guidance Rule is met, this will trigger an iSRC review to re-evaluate the benefit risk of apraglutide and thus make recommendations on the further conduct of the trial as necessary and appropriate. During a triggered iSRC review, apraglutide dosing to existing subjects, and the screening/randomization of new subjects into the trial, will be suspended until the iSRC has concluded their review.

Table 10: Toxicity Guidance Rule

Number of subjects randomized	Number of observed toxicity events triggering iSRC meeting
1–6	≥1
7–12	≥2
13–15	≥3
16–21	≥4
22–24	≥5
25–27	≥6
28–30	≥7

iSRC=independent safety review committee

7 DATA ANALYSIS AND STATISTICAL CONSIDERATIONS

7.1 General Considerations

All continuous efficacy data will be summarized descriptively by dose group and time point including changes from baseline (n, arithmetic mean, standard deviation, minimum, lower quartile [Q25], median, upper quartile [Q75], and maximum). Categorical variables will be summarized with frequencies and percentages by treatment group and time point.

From an efficacy perspective, the overall statistical aim of the trial is geared toward estimation. Thus, efficacy data collected on both the low and high doses will be compared to external data on BAT where possible using Bayesian methods to provide insight into the likelihood of efficacy vis-à-vis BAT. In this sense, statistical analysis will not focus upon p-value generation but rather estimation and quantification of uncertainty.

A SAP will be prepared and finalized prior to the final analysis. The SAP will detail the implementation of the planned statistical analyses in accordance with the principal features stated in the protocol, and will provide full details of the analyses, data displays, and algorithms to be used for data derivation.

The final analysis will be done in two steps. The primary analysis of safety and efficacy will be performed once all subjects have either completed Day 91 or withdrawn from the trial. Additional analyses will be done once all the subjects have either completed the EOT visit or withdrawn from the trial. A CTR will be issued after the primary analysis. An addendum to the CTR will cover the follow-up period until 2 years after the first apaglutide dose.

7.2 Interim analysis

An interim analysis will be performed when 17 subjects have either reached Day 56 or withdrawn from the trial. All available data points by the data cut-off date will be included in the analysis. This interim analysis does not represent a typical interim analysis with testing of hypotheses and alpha spend.

7.3 Missing, Unused, and Spurious Data

Strategies for handling missing, unused, or spurious data will be specified in the SAP.

7.4 Determination of Sample Size

The principal statistical goal of this trial from an efficacy perspective is to estimate the likelihood of efficacy of apaglutide therapy in the treatment of subjects with SR lower GI-aGVHD after alloSCT. Published, randomized control trial data on BAT in the treatment of such subjects [Zeiser, 2020a] provides estimates of overall response rate at Day 28 of 62% (96/154) and durable overall response at Day 56 of 40% (61/154). Further, the GI-aGVHD response rate at Day 28 of 57% (55/96) is also published [Zeiser, 2020b]. At the time of trial initiation, this was considered the best matched information available for a reasonable sample size determination.

Assuming same degree of decline of GI response from Day 28 to Day 56 as observed for an overall response from Day 28 to Day 56, the GI response at Day 56 can be estimated as 36% (r=35 responses in n=96 subjects). These data provide a reliable prior for the true response rate on BAT, π_r , such that $\pi_r \sim \text{Beta}(r+1, n-r+1) = \text{Beta}(36, 62)$.

In the current trial, it is planned to randomize 30 subjects on a 1:1 basis to high or low dose apaglutide. Assuming a non-informative prior for the Day 56 GI response rate with apaglutide, 15 subjects per dose will provide a posterior distribution for the true response rate with apaglutide π_a , such that $\pi_a \sim \text{Beta}(s+1, 15-s+1)$ where s is the observed number of successes on any given dose. Using the prior for BAT response, π_r , and the posterior for the apaglutide response, π_a , it is possible to construct the posterior distribution for the true difference in response rates, $\pi_a - \pi_r$.

Considering a penalty on the original assumptions that are based on Day 56 durable overall response instead of Day 56 response, one can still detect an effect of apaglutide over BAT.

At least five out of seven responders at the interim analysis will be able to detect a signal of apaglutide at least 10% greater than the Day 56 durable overall response with a probability of 88.2%.

In case of a sufficiently large response rate in a single treatment arm, the planned sample size will allow for reliable conclusions regarding the effectiveness of apaglutide relative to BAT for Day 56 response rate in the treatment of subjects with SR lower GI-aGVHD after alloSCT. Considering a penalty on the original assumptions, we can still detect an effect of apaglutide over BAT.

In addition to the N=30 subjects randomized to receive low or high doses of apaglutide once weekly for 26 weeks, a separate, non-randomized cohort of up to four subjects with body weights ranging from 40.0 to <50.0 kg will be assigned to receive 2.5 mg apaglutide (LBW dose).

7.5 Definition of Analysis Sets

7.5.1 Full Analysis Set

The Full Analysis Set (FAS) comprises all enrolled subjects (randomized and non-randomized LBWs). All efficacy evaluations will be conducted using the FAS according to the planned dose (high dose, low dose, LBW dose) and in total. All subjects will be analyzed according to the apaglutide dose assigned by randomization.

7.5.2 Low Body Weight Analysis Set

The LBW Analysis Set comprises a separate, non-randomized cohort of up to four subjects with body weights ranging from 40.0 to <50.0 kg assigned to receive 2.5 mg apaglutide (LBW dose) who receive at least one dose of therapy and who provide at least one post-baseline assessment for any secondary endpoint.

7.5.3 Safety Analysis Set 1

The Safety Analysis Set (SAS) 1 (SAS1) comprises all randomized subjects exposed to both apaglutide dose levels. All principal safety analyses of subjects randomized low or high doses of apaglutide will be carried out on the SAS1. Subjects are analyzed according to the dose of apaglutide received.

7.5.4 Safety Analysis Set 2

The SAS2 comprises all randomized and non-randomized subjects exposed to both apaglutide dose levels. Supportive safety analyses will be carried out on the SAS2. Subjects are analyzed according to the dose of apaglutide received.

7.6 Statistical Evaluation of Safety

Safety data will be summarized by randomized dose separately and combined for both SAS1 and SAS2. Safety data on apaglutide 2.5 mg in the non-randomized LBW Analysis Set will be listed and presented separately. Safety assessments include AE reporting, vital signs, 12-lead ECG, clinical laboratory evaluations, and physical examinations.

7.6.1 Adverse Events

All AESIs, treatment-emergent AEs (TEAEs), SAEs, AEs leading to discontinuation, AEs leading to death and laboratory abnormalities will be summarized by apaglutide dose received. Adverse event data will be coded using the latest version of MedDRA. A definition of TEAEs will be presented in the SAP. Treatment-emergent AEs will be summarized descriptively by apaglutide dose received, and by the frequency of subjects experiencing events corresponding to body systems and MedDRA PT.

Subjects with multiple occurrences of events will only be counted once at the maximum severity/grade to trial therapy for each PT, SOC, and overall. Should the majority of subjects experience multiple occurrences of the same event type, individual event rates of these events will be evaluated.

A summary table will be presented for each of the following AE categorizations in terms of the number and percentage of subjects experiencing AEs by SOC and PT:

- All TEAEs
- Serious TEAEs
- Treatment-emergent AEs by severity (mild/moderate/severe)
- Treatment-emergent AEs leading to withdrawal from the trial
- Treatment-emergent AEs leading to discontinuation of randomized treatment
- Treatment-emergent AEs leading to death

Furthermore, AEs will be summarized by causality and the maximum intensity. Any SAEs and/or AEs that led to withdrawal will be listed. All AEs will also be summarized by relatedness to apaglutide therapy. Adverse events that are reported as possibly, probably, or definitely related to apaglutide therapy will be counted as related to trial therapy. Adverse events with a missing relationship will be considered as “related” for this summary.

The SAP will provide detailed descriptions for the analysis of other AE information, such as duration, action taken, and clinical outcome.

7.6.2 Adverse Events of Special Interest

The individual and cumulative incidence of the following groupings AESIs will be summarized by dose:

- Injection site reactions
- Gastrointestinal obstructions
- Gallbladder, biliary, and pancreatic disease
- Fluid overload
- Colorectal polyps
- New malignancy
- Systemic hypersensitivity

The specific AE PTs falling into each of these groupings will be determined prior to randomization of the first subject and will be captured in the SAP.

7.6.3 Laboratory Results

Hematology and chemistry laboratory data will be summarized by apaglutide dose received. Clinical Laboratory evaluation results will be listed and compared to laboratory reference ranges, with those values outside of the applicable range flagged as high or low. Shift tables will be provided to examine the distribution of changed pre/post receipt of apaglutide therapy. Quantitative laboratory data will be summarized using descriptive statistics (n, arithmetic mean, median, minimum, and maximum) for each parameter by dose and time.

7.6.4 Vital Signs

Each vital sign and respective change from baseline will be summarized over time by apaglutide dose received. Subjects with clinically significant abnormalities in vital signs as compared to baseline will be listed.

7.6.5 Physical Examination

A summary table for the shift from pre-/post-trial therapy received in physical examination will be summarized over time by apaglutide dose.

7.6.6 Twelve-Lead Electrocardiogram

The ECG data will be summarized by apaglutide dose received over time using descriptive statistics for change-from-baseline values and categorical outliers. Any clinically significant changes will be recorded as AEs.

7.6.7 Anti-Drug Antibodies

All immunogenicity analyses will be descriptive and carried out with a special focus on neutralizing antibodies, and treatment-induced or treatment-boosted ADA. Impact on PK, PD, and safety will be described.

7.7 Pharmacokinetic Statistical Analysis

Apaglutide individual subject concentrations will be summarized in the FAS and the LBW Analysis Set. The PK parameters will be obtained as post-hoc estimates based on the population PK/PD analysis developed by Lyo-X. They will be reported in a dedicated separate report.

7.7.1 Population Pharmacokinetic Analysis

Apaglutide PK parameters: absorption rate constant (ka), apparent clearance (CL/F), and apparent volume of distribution (Vz/F) of apaglutide, with their intra- and inter-individual variability in the subject population, will be derived by population PK data analysis using a nonlinear mixed effects modeling approach, based on sparse sampling. These parameters will be reported in a dedicated separate report.

Trough plasma concentrations (C_{trough}) will be collected before dosing at Weeks 1, 2, 3, 4, 6, and 8. At Week 0 and Week 4 (or if not possible at Week 4, then samples should be collected at Week 5 or Week 6 or Week 7 or Week 8), samples will be collected at 6, 30, 72, 120, and 168 hours post-dose. Samples will have to be taken within ± 2 hours window, except for the 6-hour post-dose sample where samples will have to be taken within ± 1 hour window.

For every subject, visual inspection of the actual concentrations of apaglutide will be compared with a simulated PK profile based on a PK model developed on healthy volunteers and SBS patients' data from Phase I and II clinical studies. The simulated PK profile will be constructed based on the dose received and the subject's body weight. This will be performed online for every subject, and this will be used to check if the subject is correctly exposed to apaglutide.

7.8 Statistical Evaluation of Efficacy

In general, efficacy data will be summarized by randomized dose separately and combined in the FAS. Efficacy data on apaglutide 2.5 mg in the non-randomized LBW Analysis Set will be listed and presented separately.

7.8.1 Lower GI-aGVHD Response at Day 56

Overall response rate (PR and CR) at Day 56 on the lower GI tract MAGIC score was used for sample size estimation. It will be summarized descriptively and analyzed formally using Bayesian methods.

The prior for the true Day 56 lower GI response rate on BAT, π_r , and i will be based on the best matched historical control available at the time of analysis. The true response rate on BAT will be given, such that $\pi_r \sim \text{Beta}(r+1, n-r+1)$, where n is the number of subjects treated with BAT and r is the number of successes observed in the historical control. Assuming a non-informative prior for the Day 56 lower GI response rate with apaglutide, the posterior distribution for true response rate with apaglutide 5 mg, π_a , will be given as $\pi_a \sim \text{Beta}(s+1, m-s+1)$ where m is the number of subjects randomized to the 5 mg dose and s is the number of successes observed on this dose. A similar formulation applies to the 10 mg dose and for the two doses combined.

For each dose, and for doses combined, the response rate for BAT (π_r) and apaglutide (π_a) will be taken as the mean of the respective Beta distributions and the 5th and 95th percentiles will provide the associated 90% credible intervals. The difference in response rates, $\pi_a - \pi_r$, for each dose, and for the doses combined, will be taken as the difference in mean response rates. The associated 90% credible interval will be computed by sampling 100,000 pairs of random deviates from the respective Beta distributions, taking the difference of each pair (apaglutide – BAT) and extracting the 5th and 95th centiles of the resulting empirical distribution of the differences. Similarly, the probability that the true response rate is higher with apaglutide than with BAT will be taken as the fraction of differences greater than zero.

Day 56 lower GI response will also be summarized descriptively in the LBW Analysis Set using the Beta distribution. The response rate and associated 95% credible interval will be estimated and presented.

Subjects with missing data such that the Day 56 lower GI response cannot be determined will be included in the preceding analysis as non-responders consistent with intent to treat philosophy. A sensitivity analysis will also be performed based only on those subjects with non-missing data being consistent with a missing at random assumption.

To evaluate the robustness of the analysis of the Day 56 secondary endpoint, sensitivity analyses evaluating alternative response definitions taking account for the potential influence of intercurrent events like increase in steroids, development of infectious colitis, relapse, and the use of budesonide or other non-absorbable steroids will be made. Details of these analyses will be outlined in the SAP.

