4.2 Administration of Experimental and Control Interventions

4.2.1 Experimental Intervention

4.2.1.1 Administration of Apraglutide

The dose to be administered to the subject at each time point depends on the treatment arm to which the subject is randomized and the subject's weight at baseline, as presented in Table 4. Non-randomized subjects with LBWs will only receive 2.5 mg of apraglutide.

Table 4: Dose of Investigational Medicinal Product Based on Treatment Arm and Weight

Treatment Arm	Weight Band (based on Baseline Weight)			
	40.0–<50.0 kg ¹	50.0–<60.0 kg	60.0–80.0 kg	>80.0 kg
Low dose (mg)	2.5	2.5	4	5
High dose (mg)		5	7.5	10

1. A non-randomized cohort of up to four subjects

The SC injection will be administered in the abdominal area or in the thigh. The injection site must be rotated such that an injection is administered at least 5 cm away from where the last injection was administered.

The IMP must be administered weekly as per scheduled (Table 1 and Table 2). Detailed instructions will be provided in the Pharmacy Manual for the site.

The Investigator is ultimately responsible for the appropriate preparation and administration of the IMP by assigning the appropriate site personnel and ensuring they are well-trained. The dose assigned through IRT will need to remain blinded to the subjects. Investigational medicinal product will not be administered to any person not enrolled in this trial.

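### Protocol 7.8.1 defines the Day 56 Bayesian analysis groups by milligram dose (5 mg, 10 mg) although subjects are randomised to low and high arms; the groups need relabelling before any comparison with BAT is run

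*Protocol*

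**What the plan says.** Protocol 7.4 sizes the trial on two randomised arms: "it is planned to randomize 30 subjects on a 1:1 basis to high or low dose", and "15 subjects per dose will provide a posterior distribution for the true response rate", in the form Beta(s+1, 15-s+1).

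Protocol 4.2.1.1 states that the administered dose "depends on the treatment arm to which the subject is randomized and the subject's weight at baseline". Table 4 gives the low arm 2.5, 4 and 5 mg and the high arm 5, 7.5 and 10 mg, in the bands 50 to <60 kg, 60 to 80 kg and >80 kg.

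Protocol 7.8.1 then writes the apraglutide posterior as Beta(s+1, m-s+1), where "m is the number of subjects randomized to the 5 mg dose" and s is the number of responders on that dose. It continues: "A similar formulation applies to the 10 mg dose and for the two doses combined". Protocol 7.8.2 analyses the other binary secondary endpoints in the same way.

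Protocol 7.5.1 groups efficacy evaluations "according to the planned dose (high dose, low dose, LBW dose) and in total". The synopsis, 7.1 and the opening of 7.8 also group by arm or randomised dose. SAP 4.1 and 4.2.1 use High Dose, Low Dose, Total Randomized, Low Body Weight and Total, and SAP 4.3.9.2 reports Day 56 response with Clopper-Pearson intervals. SAP Section 6 item 7 says the comparison with external BAT data was not planned for the Primary Analysis. None of the twelve items in that section mentions the 5 mg and 10 mg wording.

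**The concern.** Section 7.8.1 is where m and s are defined, so it is the text a programmer would implement. The groups it names are not the randomised groups. In Table 4, 5 mg is both the low-arm dose above 80 kg and the high-arm dose at 50 to <60 kg, while 10 mg occurs only in the high arm above 80 kg. The doses 2.5, 4 and 7.5 mg are not covered for randomised subjects; 7.8.1 mentions the non-randomised low-body-weight set separately.

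Applied literally, the 5 mg posterior would mix the arms, each posterior would rest on fewer subjects than the planned 15, and the combined posterior would omit part of the randomised population. The statement in 7.4 that the planned sample size supports conclusions about a single treatment arm would not carry over to these groups.

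**Working it through.** **1. The plan's own figure.** Inputs from 7.4: 5 responders of 7, giving Beta(6, 3) under a uniform prior; BAT 35 of 96, giving Beta(36, 62); margin 0.10. The 35 checks: 55/96 × 61/96 = 0.364, and 0.364 × 96 = 34.9, rounded to 35. Numerical integration of P(π_a > π_r + 0.10) gives 88.6%, against 88.2% stated. The figure is reproduced closely. It depends only on 5/7 and 35/96, so the labelling in 7.8.1 does not affect it.

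**2. Group sizes under the literal reading.** Let w1, w2 and w3 be the shares of subjects at 50 to <60, 60 to 80 and >80 kg, taken as equal in both arms with 15 per arm. The documents do not give these shares.

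- 5 mg: 15·w3 (low arm) + 15·w1 (high arm)
- 10 mg: 15·w3 (high arm)
- In neither group: 15·w1 (2.5 mg) + 15·w2 (4 mg) + 15·w2 (7.5 mg) = 15·(1 + w2 − w3)

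| Assumed shares w1/w2/w3 | 5 mg (low + high arm) | 10 mg | Left out of 30 |
|---|---|---|---|
| equal thirds | 10 (5 + 5) | 5 | 15 |
| 20/50/30% | 7.5 (4.5 + 3) | 4.5 | 18 |
| 10/50/40% | 7.5 (6 + 1.5) | 6 | 16.5 |
| 30/50/20% | 7.5 (3 + 4.5) | 3 | 19.5 |

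Half or more of the randomised subjects are left out whenever w2 is at least w3. Fewer are left out if the >80 kg band is larger than the 60 to 80 kg band.

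**3. Effect on precision.** The posterior is Beta(s+1, m−s+1), the 90% interval runs from its 5th to its 95th percentile, and the BAT prior is Beta(36, 62). All rows take 60% observed response.

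| Group | s/m | 90% interval width | P(π_a > π_r) |
|---|---|---|---|
| One arm, as planned | 9/15 | 0.38 | 0.956 |
| Literal 5 mg, equal thirds | 6/10 | 0.45 | 0.925 |
| Literal 10 mg, equal thirds | 3/5 | 0.58 | 0.856 |
| Both arms combined, as planned | 18/30 | 0.28 | 0.988 |

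With equal thirds the literal combined group is 10 + 5 = 15 subjects, so at 9/15 its interval is as wide as that of one planned arm (0.38) instead of 0.28.

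**The case against.** The intended grouping is plain. The synopsis, 7.1, 7.4, 7.5.1 and the opening of 7.8 all point to arms. Only two randomised groups exist, so a reference to two doses to which subjects are randomised most naturally means low and high. Section 1.6 argues the dose rationale around 5 mg and 10 mg, and these are the top doses of the two arms in Table 4. The wording therefore looks like an uncorrected nominal label. The SAP already reports by arm, omits the BAT comparison from the Primary Analysis, and specifies no Bayesian comparison at any step, so no output it currently specifies would change.

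All of this stands, and it limits the point to a labelling error. It does not make the text safe. SAP Section 6 item 7 concerns the Primary Analysis only. SAP Section 1 says endpoints are analysed at both steps unless specified otherwise, and Protocol 1.9 and 2.1 keep open the search for a better-matched control. If one is found, for example for the EOT analysis, 7.8.1 is the only specification to run from.

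Two stronger readings should be resisted. A reader might infer that the comparison loses the benefit of randomisation. But 7.8.1 contains no dose-against-dose contrast: every difference is apraglutide minus a historical control that was never randomised, and SAP Section 6 item 12 rules out a formal comparison of the dose groups. A reader might also turn the smaller groups into a lower chance of success. The plan adopts no posterior threshold and no assumed true response rate for 7.8.1. The 88.2% describes one possible interim result, and a chance computed from an invented threshold would not fall steadily with m because the counts are discrete.

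**Conclusion.** Protocol 7.8.1 is wrong as written: its groups do not match the randomisation, the sample-size section or the analysis-set definition. The documents do not support reading it as a deliberate per-milligram analysis, or as one that will discard subjects from the Primary Analysis. The consequence is conditional. It arises only if the Bayesian comparison, or the 7.8.2 binary endpoints analysed in the same way, is run from 7.8.1. In that case about 15 to 20 of 30 randomised subjects would be left out over the weight distributions tried above, and the intervals would widen as shown. Those sizes rest on assumed weight shares, equal in both arms, and on an illustrative 60% response. The contradiction itself rests on no assumption. The sample-size figure is unaffected.

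**What to change.** In Protocol 7.8.1, define m as all FAS subjects randomised to the low-dose arm, across the three weight bands, and s as the responders among them. Define the high-dose arm in the same way (planned 15 each), and define combined as all randomised subjects (planned 30). Drop the references to 5 mg and 10 mg from the formula text. Add one item to SAP Section 6 recording this clarification, so that it governs any later comparison with BAT and the binary endpoints under 7.8.2.

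The cost is a few words in the protocol and one sentence in the SAP. No data, subjects or procedures are added. The change concerns analysis groups only and says nothing about dosing.
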